4.7 TREATMENT/ DOSE MODIFICATIONS

4.7.1 Ribociclib - Dose Modification Guidelines

Management of severe or intolerable adverse reactions requires temporary dose reduction and/or interruption of ribociclib therapy. For patients who do not tolerate the dosing schedule, dose adjustments are permitted in order to allow the patient to continue the study treatment.

	Ribociclib dose	Number of capsules/tablets
		& strength
Starting dose	600 mg	3 x 200 mg
		capsules/tablets
First dose reduction	400 mg	2 x 200 mg
		capsules/tablets
Second dose reduction	200 mg	1 x 200 mg
		capsules/tablets

4.7.1.1 Ribociclib Dose Adjustment/Management Recommendation for Hematological Adverse Reactions

Toxicity/Grade	Dose Adjustment and Management Recommendations
Thrombocytopenia	
Grade 1(≥75 x10 ⁹ /L)	No dose adjustment required.

Grade 2 (≥50 x 10 ⁹ /L − <75 x 10 ⁹ /L)	Dose interruption until recovery to grade <2
	Re-initiate ribociclib at the same dose.
Grade 3 (≥25 x 10 ⁹ /L - <50 x 10 ⁹ /L)	Dose interruption until recovery to grade <2.
	Re-initiate ribociclib at the same dose level.
	If toxicity recurs at grade 3: temporary dose
	interruption until recovery to grade 1 and reduce
	ribociclib to the next lower dose level.
Grade 4(<25 x 10 ⁹ /L)	Dose interruption until recovery to grade <2.
	Re-initiate ribociclib at the next lower dose level.
	If toxicity recurs at grade 4: discontinue ribociclib
Absolute neutrophil count (ANC)	
Grade 1 (≥1.5 x10 ⁹ /L)	No dose adjustment required.
Grade 2 (≥1.0 - <1.5 x 10 ⁹ /L)	No dose adjustment required.
Grade 3 (≥0.5 - <1.0 x 10 ⁹ /L)	Dose interruption until recovery to $\geq 1.0 \times 10^9/L$.
	Re-initiate ribociclib at the same dose level.
	If toxicity recurs at grade 3: temporary dose
	interruption until recovery to ≥1.0 x 10 ⁹ /L.
	If resolved in ≤7 days, then maintain dose level.
	If resolved in >7 days, then reduce ribociclib dose
	to the next lower dose level.
Grade 4 (<0.5 x 10 ⁹ /L)	Dose interruption until recovery to ≥1.0 x 10 ⁹ /L.
	Re-initiate ribociclib at the next lower dose level.
	If toxicity recurs at grade 4: temporary dose
	interruption until
	recovery to ≥1.0 x 10 ⁹ /L and reduce ribociclib
	at the next lower dose level.

Febrile neutropenia	
Grade 3 ANC <1.0 x 10 ⁹ /L with a single temperature of >38.3 ^o C (101 ^o F) or a sustained temperature of ≥38 ^o C (100.4 ^o F) for more than one hour	Dose interruption until improvement of ANC ≥1.0 x 10 ⁹ /L and no fever. Restart at the next lower dose level. If febrile neutropenia recurs, discontinue ribociclib.
Grade 4	Discontinue ribociclib.

Life-threatening	
consequences; urgent	
intervention indicated	
Anemia	
(Hemoglobin)	
Grade 1 (≥10.0 – LLN g/dL)	No dose adjustment required.
Grade 2 (≥8.0 – <10.0 g/dL)	No dose adjustment required.
Grade 3 (<8.0 g/dL)	Dose interruption until recovery to grade <2.
	Re-initiate ribociclib at the same dose.
Grade 4	Discontinue ribociclib.
Life-threatening	
consequences; urgent	
intervention indicated	

4.7.1.2 Recommendations for Ribociclib Dose Modification in Case of Hepatic Toxicities

HEPATOTOXICITY (BILIRUBIN, SGPT/ALT, SGOT/AST)		
TOTAL BILIRUBIN without ALT/AST increase above baseline value		
Grade 1 (> ULN – 1.5 x ULN)	Maintain dose level with LFTs monitored every	
(confirmed 48 to 72hrs later)	two weeks	
Grade 2 (>1.5 – 3.0 x ULN)	Dose interruption of ribociclib	
	If resolved to ≤ grade 1 in ≤21 days, then maintain dose level	
	If resolved to ≤ grade 1 in >21 days or toxicity recurs, then reduce 1 dose level	
	Repeat liver enzymes and bilirubin tests twice	
	weekly for 2 weeks after dose resumption	
	If toxicity recurs after two dose reductions,	
	discontinue ribociclib	
Grade 3 (>3.0 – 10.0 x ULN)	Dose interruption of ribociclib	
	If resolved to ≤ grade 1 in ≤21 days, lower 1 dose level of ribociclib	
	Repeat liver enzymes and bilirubin tests twice weekly for 2 weeks after dose resumption	
	If resolved to ≤ grade 1 in >21 days or toxicity	
	recurs, discontinue ribociclib	
Grade 4 (>10.0 x ULN)	Discontinue ribociclib	

Confounding factors and/or alternative causes for increase of total bilirubin should be excluded before dose interruption/reduction. They include but are not limited to: evidence of obstruction, such as elevated ALP and GGT typical of gall bladder or bile duct disease, hyperbilirubinemia due to the indirect component only (i.e. direct bilirubin component ≤1 x ULN) due to hemolysis or Gilbert Syndrome, pharmacologic treatment, viral hepatitis, alcoholic or autoimmune hepatitis, other hepatotoxic drugs.

For patients with Gilbert Syndrome, these dose modifications apply to changes in direct bilirubin only. Bilirubin will be fractionated if elevated.

HEPATOTOXICITY (BILIRUBIN, SGPT/ALT, SGOT/AST)		
AST or ALT		
AST or ALT without bilirubin elevation >2 x ULN		
Same grade as baseline or increase from baseline grade 0 to grade 1 (confirmed 48 to 72 hrs later)	No dose adjustment required with LFTs monitored per protocol if same grade as baseline or every two weeks in case of increase from baseline grade 0 to 1	
Increase from baseline grade 0 or 1 to grade 2 (>3.0 – 5.0 x ULN)	Dose interruption of ribociclib If resolved to ≤ baseline value in ≤21 days, then maintain dose level If resolved to ≤ baseline value in >21 days or toxicity recurs, then reduce 1 dose level Repeat liver enzymes and bilirubin tests twice weekly for 2 weeks after dose resumption If toxicity recurs after two dose reductions or recovery to ≤ baseline value is >28 days, discontinue ribociclib	
Increase from baseline grade 0 or 1 to grade 3 (>5.0 – 20.0 x ULN)	Dose interruption of ribociclib until resolved to ≤ baseline value, then lower 1 dose level of ribociclib Repeat liver enzymes and bilirubin tests twice weekly for 2 weeks after dose resumption If recovery to ≤ baseline value is >28 days, discontinue ribociclib If toxicity recurs, discontinue ribociclib	

Increase from baseline grade 2 to grade 3 (>5.0 – 20.0 x ULN)	Dose interruption of ribociclib until resolved to ≤ baseline value, then lower 1 dose level of ribociclib Repeat liver enzymes and bilirubin tests twice weekly for 2 weeks after dose resumption If toxicity reoccurs after 2 dose reductions or recovery to ≤ baseline value is > 28 days, discontinue ribociclib
Grade 4 (>20.0 x ULN)	Discontinue ribociclib
AST or ALT and concurrent Bilirubin	Discontinue Hibociciii
For patients with normal ALT or AST or total bilirubin at baseline: AST or ALT ≥ grade 2 combined with total bilirubin >2 x ULN without evidence of cholestasis or For patient with elevated AST or ALT or total bilirubin at baseline: baseline: [AST or ALT >2 x baseline AND >3.0x ULN] OR [AST or ALT 8.0x ULN]- whichever is lower-combined with [total bilirubin 2x baseline AND >2.0 x ULN]	

Confounding factors and/or alternative causes for increased transaminases should be excluded before dose interruption/reduction. They include but are not limited to: concomitant medications, herbal preparations or dietary supplements, infection, hepatobiliary disorder or obstruction, new or progressive liver metastasis, and alcohol intake.

Additional Follow-up for Hepatic Toxicities

Increase in transaminases combined with total bilirubin (TBIL) increase may be indicative of drug induced liver injury (DILI), and should be considered as clinically important events.

The threshold for potential DILI may depend on the patient's baseline AST/ALT and TBIL value; patients meeting any of the following criteria will require further follow-up as outlined below:

For patients with normal ALT or AST or TBIL value at baseline: AST or ALT > 3.0 x
 ULN combined with TBIL > 2.0 x ULN

For patients with elevated AST or ALT or TBIL value at baseline: [AST or ALT > 2 x baseline AND > 3.0 x ULN] OR [AST or ALT > 8.0 x ULN], whichever is lower, combined with [TBIL > 2 x baseline AND > 2.0 x ULN]

Medical review needs to ensure that liver test elevations are not caused by cholestasis, defined as: ALP elevation > 2.0 x ULN with R value < 2 in patients without bone metastasis, or elevation of ALP liver fraction in patients with bone metastasis.

Note: (The R value is calculated by dividing the ALT by the ALP, using multiples of the ULN for both values. It denotes the relative pattern of ALT and/or ALP elevation is due to cholestatic or hepatocellular liver injury or mixed type injury)

In the absence of cholestasis, these patients should be immediately discontinued from study drug treatment, and repeat LFT testing as soon as possible, preferably within 48 hours from the awareness of the abnormal results. The evaluation should include laboratory tests, detailed history, physical assessment and the possibility of liver metastasis or new liver lesions, obstructions/compressions, etc.

Hepatic toxicity monitoring includes the following LFTs: albumin, ALT, AST, total bilirubin, direct and indirect bilirubin, alkaline phosphatase (fractionated if alkaline phosphatase is grade 2 or higher), creatine kinase, protrombine time (PT/INR) and GGT. For patients with Gilbert Syndrome: total and direct bilirubin must be monitored, intensified monitoring applies to changes in direct bilirubin only.

Close observation is recommended in case of AST, ALT, and/or bilirubin increase requiring dose interruption, which involves:

- Repeating liver enzyme and serum bilirubin tests two or three times weekly.
 Frequency of retesting can decrease to once a week or less if abnormalities stabilize or return to normal values.
- Obtaining a more detailed history of current symptoms.
- Obtaining a more detailed history of prior and/or concurrent diseases, including history of any preexisting liver conditions or risk factors.
- Obtaining a history of concomitant drug use (including non-prescription medications, herbal and dietary supplements), alcohol use, recreational drug use, and special diets.
- Ruling out acute viral hepatitis types A, B, C, D, and E; hepatotropic virus infections (CMV, EBV or HSV); autoimmune or alcoholic hepatitis; NASH; hypoxic/ischemic hepatopathy; and biliary tract disease.
- Obtaining a history of exposure to environmental chemical agents.
- Obtaining additional tests to evaluate liver function, as appropriate (e.g., INR, direct bilirubin).
- Considering gastroenterology or hepatology consultations.
- Assessing cardiovascular dysfunction or impaired liver oxygenation, including hypotension or right heart failure as possible etiologies for liver dysfunction.

• Liver biopsy as clinically indicated to assess pathological change and degree of potential liver injury.

All cases confirmed on repeat testing meeting the laboratory criteria defined above, with no other alternative cause for LFT abnormalities identified, should be considered as "medically significant", thus met the definition of SAE (Section 7.02), and reported as SAE using the term "potential drug-induced liver injury". All events should be followed up with the outcome clearly documented.

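### In 4.7.1.2 a small ALT/AST rise switches off every bilirubin row, so bilirubin above 1.5 x ULN with an ALT/AST rise short of the combined stopping row gets no dose adjustment, or no hepatic row at all

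*Combined protocol and SAP*

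**What the plan says.** Section 4.7.1.2 has three blocks.

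- **Bilirubin rows**, headed "TOTAL BILIRUBIN without ALT/AST increase above baseline value". Grade 2 (above 1.5 to 3.0 x ULN) means interrupt; grade 3 (above 3.0 to 10.0) means interrupt and restart one level lower; grade 4 (above 10.0) means discontinue. The grade 2 row adds "If resolved to ≤ grade 1 in >21 days or toxicity recurs, then reduce 1 dose level". The grade 3 row reads "If resolved to ≤ grade 1 in ≤21 days, lower 1 dose level of ribociclib", and discontinues if recovery takes longer or toxicity recurs. Both ask for retesting after restart: "Repeat liver enzymes and bilirubin tests twice weekly for 2 weeks after dose resumption".
- **AST/ALT rows**, headed "AST or ALT without bilirubin elevation >2 x ULN". The first row covers ALT/AST in its baseline grade or going from grade 0 to 1: "No dose adjustment required with LFTs monitored per protocol if same grade as baseline", with two-weekly tests after a move from grade 0 to 1.
- **A combined row.** For a normal baseline it needs ALT/AST grade 2 or higher with bilirubin above 2 x ULN and no cholestasis. For a raised baseline it needs ALT/AST above 2 x baseline and above 3 x ULN, or the 8 x ULN alternative, with bilirubin at twice baseline and above 2 x ULN. The follow-up text in the same section makes the action immediate discontinuation.

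The follow-up text also says: "Close observation is recommended in case of AST, ALT, and/or bilirubin increase requiring dose interruption", with liver tests two or three times weekly. Section 4.7.1.5 holds a table for all other adverse reactions.

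**The concern.** The condition on the bilirubin rows has no minimum size. An ALT that moves from 0.5 to 0.9 x ULN is an increase above baseline, so every bilirubin row, including the grade 4 stop, ceases to apply. The combined row does not take over until ALT/AST is much higher.

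This runs against the protocol's own view of risk. Section 4.7.1.2 says that transaminases and bilirubin rising together may point to drug-induced liver injury. Section 4.6 counts grade 2 or higher bilirubin lasting more than 7 days, or any grade 3 or higher bilirubin, as a DLT with no condition on ALT. A lead-in patient could therefore be in the no-adjustment row on a bilirubin value that becomes a DLT if it persists. What is at stake is patient safety and consistent dosing across about 25 centers.

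**Working it through.** The check applies the three sets of row conditions to the same patient.

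**Inputs.** All limits are in multiples of ULN and come from Section 4.7.1.2. Section 3.1 (inclusion 11) allows baseline ALT/AST below 2.5, or below 5 with liver metastases. Assumptions: baseline bilirubin below ULN, no Gilbert's syndrome, no cholestasis, and ALT grade 1 running from ULN to 3.0 (the section gives only the start of grade 2, above 3.0).

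**Conditions for a row to match.**

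- Bilirubin rows: ALT/AST at or below baseline.
- AST/ALT rows: bilirubin at or below 2.0.
- Combined row, normal baseline: ALT/AST above 3.0 and bilirubin above 2.0.

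If ALT is above baseline but not above 3.0 and bilirubin is above 2.0, all three conditions fail. If bilirubin is above 1.5 and up to 2.0, only the AST/ALT block is left.

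| ALT, baseline to now | Bilirubin | Same bilirubin, ALT unchanged (bilirubin row) | Hepatic row as written | With the fix |
|---|---|---|---|---|
| 0.5 to 1.5 | 1.8 | interrupt | no adjustment | interrupt |
| 2.0 to 2.8 | 1.8 | interrupt | no adjustment | interrupt |
| 4.0 to 4.5 (liver metastases) | 1.8 | interrupt | no adjustment | interrupt |
| 0.5 to 1.5 | 2.5 | interrupt | none | interrupt |
| 0.5 to 1.5 | 5 | interrupt, lower one level | none | interrupt, lower one level |
| 0.5 to 1.5 | 12 | discontinue | none | discontinue |
| 0.8 to 3.5 | 1.8 | interrupt | interrupt | interrupt |
| 0.8 to 6 | 1.8 | interrupt | interrupt, lower one level | interrupt, lower one level |
| 0.8 to 3.5 | 2.5 | interrupt | discontinue | discontinue |
| 0.8 to 3.5 | 5 | interrupt, lower one level | discontinue | discontinue |

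The first three rows are the milder instruction, the next three have no hepatic row, and the last four are as strict as bilirubin alone or stricter.

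**Monitoring in the first three rows.** Interruption brings close observation: 2 weeks x 2 or 3 tests = 4 to 6 tests in two weeks, before any step-down once values stabilize. The no-adjustment row gives 1 test in two weeks after a move from grade 0 to 1, besides the confirmation at 48 to 72 hours. If the grade is unchanged it gives only the protocol schedule, which in Section 6.5 is chemistry on day 1 of each 28-day cycle.

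**What 4.7.1.5 supplies in the no-row cases.**

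| | Bilirubin block | 4.7.1.5 |
|---|---|---|
| Grade 2, first action | interrupt, same dose if recovered in 21 days | interrupt, same dose |
| Grade 3, first action | interrupt, lower one level | interrupt, lower one level |
| Grade 4 | discontinue | discontinue |
| Time limit on recovery | 21 days | none |
| Recurrence after grade 3 | discontinue | reduce if grade 2, discontinue if grade 3 |
| Tests after restart | twice weekly for 2 weeks | not specified |

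**The case against.** **The combined row already handles joint rises.** A reader might infer that any patient in whom both values rise is treated more leniently. The documents do not support that: the last two rows of the first table show discontinuation where bilirubin alone would mean interruption. This objection stands and limits the point to rises that miss the combined criteria.

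**The no-row patients are not left without instruction.** A reader might also infer that above 2 x ULN the protocol is silent. A catch-all table needs no cross-reference, the first actions in 4.7.1.5 match, and its interruption brings close observation too. This largely stands. What is lost is the last three lines of the second table. On recurrence, the bilirubin row names no grade, so stopping on a grade 2 recurrence is the plain reading but not an explicit one.

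**No adjustment for ALT need not mean no adjustment for bilirubin.** That answers one apparent conflict. With bilirubin 1.8 x ULN and ALT unchanged, the bilirubin row says interrupt, and the ALT row answers only the ALT result. It answers the 1.5 to 2.0 x ULN gap less well. There the bilirubin row has gone, and the AST/ALT block is written to include bilirubin up to 2 x ULN, so a site finds its case described and is told not to adjust. Nothing says that 4.7.1.5 overrides this.

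**Investigators may act anyway.** Section 6.5 (note f) allows unscheduled tests and Section 9.1 allows stopping on judgment. True, but the written rule still points the wrong way.

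**Conclusion.** The point holds for ALT/AST above baseline where the combined criteria are not met. At bilirubin above 1.5 to 2.0 x ULN, with ALT/AST in its baseline grade or moving from 0 to 1, the instruction is milder than for bilirubin alone. Above 2 x ULN the hepatic rows drop out and a similar but thinner generic table remains. The first is the more serious, because an explicit row gives the milder answer.

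The edge is clear for a normal baseline without cholestasis. For a raised baseline it depends on how the two baseline groups are read. ALT going from 4.0 to 6 x ULN with bilirubin 2.5 x ULN has no hepatic row if the groups are exclusive, because 6 is below 2 x 4.0 = 8. It means discontinuation if a normal bilirubin alone puts the patient in the normal group. The finding does not rest on that choice.

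The number of patients affected is unknown. Section 1.6 reports increased ALT in 21.3% of 47 phase Ib patients, but the documents give no frequency for the joint pattern. The primary test, its error rates and the sample size are not affected. This is a safety clarification that should be made.

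**What to change.** 1. Change the bilirubin heading so that its rows apply whatever the ALT/AST, and the AST/ALT heading so that its rows apply whatever the bilirubin, in both cases whenever the concurrent AST/ALT-and-bilirubin criteria are not met.
2. Add one sentence: *If a bilirubin row and an AST/ALT row both apply, follow the stricter action and, for recovery, meet both recovery criteria.* Both criteria are needed because bilirubin must recover to grade 1 or lower and ALT/AST to its baseline value.

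Leave the combined row, its baseline groups, the cholestasis wording and the SAE trigger for drug-induced liver injury as they are. The added sentence ranks only a bilirubin row against an AST/ALT row. It should not be used to choose between interruption and discontinuation for a patient with raised, unchanged baseline ALT/AST. Whether the combined row is met there is a clinical question for the sponsor.

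Cost: two headings and one sentence, with no extra patients. Some patients with small joint rises will be interrupted and retested, as already happens when bilirubin rises alone.

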4.7.1.3 Dose Modification Guidance in Case of QT Prolongation

Grade	Dose Modification
For All Grades	 Check the quality of the ECG and the QT value and repeat if needed. Perform analysis of serum electrolytes (K+, Ca++, Phos, Mg++). If outside of the normal range, interrupt ribociclib administration, correct with supplements or appropriate therapy as soon as possible, and repeat electrolytes until documented as normal. Review concomitant medication usage for the potential to inhibit CYP3A4 and/or to prolong the QT interval. Check compliance with correct dose and administration of ribociclib. Consider collecting a time matched PK sample; record date and time of last study drug intake
1 QTcF 450-480 ms	Perform steps 1-4 as directed in "For All Grades." No dose adjustment required.
2 QTcF 481-500 ms	Interrupt ribociclib. Perform steps 1-4 as directed in "For All Grades." Perform a repeat ECG within one hour of the first QTcF of ≥ 481 ms. Repeat ECG as clinically indicated until the QTcF returns to < 481 ms, Restart ribociclib with dose reduced by 1 dose level. Refer to Section 4.7.1 for dosing schedule. If QTcF ≥ 481 ms recurs, ribociclib should be reduced again by 1 dose level. Repeat ECGs 7 days and 14 days after dose resumption (then as clinically indicated) for any patients who had therapy interrupted due to QTcF ≥ 481 ms.
3 QTcF ≥ 501 ms on at least two separate ECGs	 Interrupt ribociclib. Perform steps 1-4 as directed in "For All Grades." Perform a repeat ECG within one hour of the first QTcF of ≥ 501 ms. If QTcF remains ≥ 501 ms, consult with a cardiologist (or qualified specialist) and repeat cardiac monitoring as indicated until the QTcF returns to < 481 ms. If QTcF returns to < 481 ms, ribociclib will be reduced by 1 dose level. Refer to Section 4.7.1 for dosing schedule. If QTcF remains ≥ 481 ms after performing steps 1-4 as directed in "For All Grades," discontinue ribociclib. Repeat ECGs 7 days and 14 days after dose resumption (then as clinically indicated) for any patients who had therapy interrupted due to QTcF ≥ 501 ms If QTcF of ≥ 501 ms recurs, discontinue ribociclib.
4 [QT/QTcF ≥ 501 or > 60 ms change from baseline] and [Torsades de pointes or polymorphic ventricular tachycardia, or signs/symptoms of serious arrhythmia]	Discontinue ribociclib. Perform steps 1-4 as directed in "For All Grades." Obtain local cardiologist (or qualified specialist) consultation and repeat cardiac monitoring as indicated until the QTcF returns to <481 ms.

4.7.1.4 Dose Adjustment and Management Recommendation for ILD/pneumonitis (CTCAE v4.03)

Grade	Dose Adjustment and Management Recommendations
1 (asymptomatic)	No dose adjustment required. Initiate appropriate medical therapy and monitor as clinically indicated.
2 (symptomatic)	Interrupt ribociclib dose until recovery to Grade ≤1, then resume ribociclib at the next lower dose level*.
3 and 4 (severe)	Discontinue ribociclib

^{*} An individualized benefit-risk assessment should be performed before resuming ribociclib

4.7.1.5 Guidance for Management of All Other Adverse Reactions

Consider performing an analysis of serum potassium, calcium, phosphorus, and magnesium for all adverse reactions that are potentially associated/aggravated with electrolyte imbalance (e.g. diarrhea, nausea/vomiting, non-QT related cardiovascular events). If electrolyte values are below the lower limit of normal, interrupt ribociclib administration, correct electrolytes with supplements as soon as possible, and repeat electrolyte testing until documented normalization of the electrolytes.

Ribociclib Dose Adjustment and Management Recommendation for All Other Adverse Reactions

Grade	Dose Adjustment and Management Recommendations
1	No dose adjustment recommended. Initiate appropriate medical therapy and monitor.
2	Dose interruption until recovery to grade ≤1. Initiate appropriate medical therapy and monitor. Re-initiate ribociclib at the same dose. • If the same toxicity recurs at grade 2, interrupt ribociclib until recovery to grade ≤1. Reinitiate ribociclib at the next lower dose level.
3	Dose interruption until recovery to grade ≤1. Initiate appropriate medical therapy and monitor. Re-initiate ribociclib at the next lower dose level. • If toxicity recurs at grade 2: temporary dose interruption until recovery to grade ≤1 and reduce ribociclib dose the next lower dose level. • If toxicity recurs at grade 3, discontinue ribociclib.
4	Discontinue ribociclib and treat with appropriate medical therapy.

